6.1 Potential Risks

Cholestyramine is a bile acid sequestrant that works by increasing the removal of bile acids from the body. The most common adverse reaction is constipation but most instances are mild, transient and controlled with conventional therapy. Other less frequent adverse reactions are abdominal discomfort, flatulence, nausea, vomiting and bleeding tendencies due to hypoprothrombinemia if use long term. Detailed information can be found on the drug leaflet attached at the appendix. Solomon et al. reported all patients tolerated cholestyramine without inordinate difficulty with 2 patients experienced hyperdefecation for a couple of days and all patients complained of the taste of the powders¹¹.

Prednisolone is a corticosteroid and work by modifying the body's immune to various conditions and decreasing inflammation. response In hyperthyroidism it reduces the conversion of T_4 to T_3 . The common adverse reactions include fluid retention, alteration in glucose tolerance, elevation in blood pressure, behavioural and mood changes, increased appetite and weight gain. There is a risk of hypothalamic-pituitary-adrenal axis suppresion and Cushing's syndrome if given long term. It may increase the risks related to infection but rate of occurrence increases with the dose of steroids. There may be an increase risk of peptic ulcer disease. If used long term may decrease bone density. In a meta analysis, the use of prednisone 35 mg daily for a mean 64 days increased the risk for diabetes (OR 1.7 (1.1-2.6) P= 0.02), hypertension (OR 2.2 (1.4-3.8) P =0.01), dermatologic effects (OR 4.5 (3.5-5.7) P= 0.001) but was not statistically significant association for peptic ulcer, bacterial sepsis, osteoporosis, psychosis and tuberculosis¹⁹. Steroids may cause muscle weakness from renal potassium loss and myopathy if taken long term but there are case reports of thyrotoxic periodic paralysis soon after glucocorticoid administration²². The detailed information regarding risks and adverse reactions to prednisolone can be found in the drug leaflet attached in the appendix.

The immediate risks foreseeable in this study would be the risk of iatrogenic hypothyroidism. However this risk is closely monitored and the event of

iatrogenic hypothyroidism action will be taken. The long-range risks would be the possibility of suppresion of the adrenal axis from the prolonged steroid use. However, this risk would be minimised as the prednisolone dose would be tapered over time.

6.2 Potential Benefits

Cholestyramine is a bile acid sequestrant that decreases the enterohepatic circulation of thyroid hormones in subjects with overt hyperthyroidism. Solomon, Kaykhaei, Mercado and Tsai et al. have all demonstrated that Cholestyramine is effective in reducing thyroid hormones with minimal side effects when added to standard therapy for up to 4 weeks of treatment. Although the common side effect is constipation, it may prove useful in hyperthyroid patients with hyperdefecation.

Prednisolone reduces the conversion of T_4 to T_3 in the circulation. Prednisolone 30 mg daily used short term effectively normalised thyroid hormone levels in 2 weeks in a series of 4 cases prior to subtotal thyroidectomy. No adverse reactions reported in this case series. In a similar study using betamethasone 0.5 mg 6 hourly coupled with iopanoic acid (500 mg 6 hourly) and propanolol for 5 days as preparation for hyperthyroid patients for surgery, drug tolerance was excellent with no serious side effects noted even in pregnant patients and no anesthetic incidents or post operative complications.

This study conducted with Cholestyramine or Prednisolone as adjunctive therapy is short term (4 weeks) and therefore minimise long term side effects of both drugs and minimise the risk of iatrogenic hypothyroidism. It has the potential to rapidly reduce thyroid hormones in a short span of time thus achieving euthyroidism promptly, improving thyrotoxic symptoms especially those with severe hyperthyroidism, the elderly and those complicated with fast atrial fibrillation and thyrotoxic cardiomyopathy. It may be useful in preoperative or pre radioactive iodine treatment where there is a need to achieve euthyroidism to prevent risks of thyrotoxic crisis. Prednisolone is readily available in most hospitals in Malaysia and fairly cheap.

This study will provide definitive efficacy and safety information of both

Cholestyramine and Prednisolone as adjunctive treatment in patients with overt hyperthyroidism. The overall benefits of this study outweigh the potential risks.

7 OBJECTIVES

7.1 Primary objectives:

1. To assess the efficacy between Cholestyramine plus standard treatment (Carbimazole plus Propanolol), Prednisolone plus standard treatment and standard treatment alone in subjects with overt hyperthyroidism

7.2 Secondary objective(s):

1. To assess the safety profile of Cholestyramine plus standard treatment, Prednisolone plus standard treatment and standard treatment alone.

8 STUDY DESIGN

8.1 Overall study design

This a multi-center, open-label, randomised, parallel-group study to compare the efficacy of cholestyramine plus standard treatment versus prednisolone plus standard treatment versus standard treatment alone in the treatment of overt hyperthyroidism. The allocation ratio is 1:1:1.

Group 1: Cholestyramine plus standard treatment

Cholestyramine powder 4g BD, Tablet Carbimazole 30 mg OD, Tablet Propanolol 40 mg BD for 4 weeks

Group 2: Prednisolone plus standard treatment

Tablet Prednisolone 30 mg OD for week 1, 20 mg OD for week 2, 10 mg OD for week 3 and 5 mg OD for week 4, Tablet Carbimazole 30 mg OD, Tablet Propanolol 40 mg bd for 4 weeks

Group 3: Standard Treatment alone

Tablet Carbimazole 30 mg OD, Tablet Propanolol 40 mg BD for 4 weeks

8.2 Schematic diagram of study design:

8.3 Discussion of study design

All hyperthyroid subjects secondary to Graves disease identified at endocrine, endocrine surgery, general medical clinics and medical wards in Hospital Putrajaya, Hospital Queen Elizabeth II and Hospital Ampang will be screened from May 2017/ Upon approval from MREC to 31st December 2017. Potential participants will be invited to a screening visit.

Screening visit

The screening visit consists of providing information about the study, obtaining informed consent and screening assessment. The investigator will further explain the study, answer any questions and seek informed consent. All subjects will provide written informed consent to their participation in the study. The subject will then have a complete history taking, clinical examination and anthropometric measures. They will have their blood sampled, approximately 10 ml for screening tests. Subjects are eligible for the trial, if they comply with the following inclusion and exclusion criteria.

Baseline visit and Randomisation

Subjects eligible for the trial will return for baseline assessment and randomisation. They will be assigned a unique sequentially numbered study identifier according to the order in which he or she is enrolled in the trial.

The subject will then complete the baseline assessment including history taking, clinical examination, anthropometric measures, blood sampling (6 ml) and imaging (if not done previously). Following baseline assessment, subjects will be randomised into either of the 3 treatment groups. A subject will be randomly allocated to one of the three treatments per random allocation sequence that will be generated by a member of the study team.

Duration

The total trial duration is expected to be 7 weeks (1 weeks screening period, 4 weeks intervention period and 2 weeks follow up period). The intervention period for each subject will be 4 weeks. The subject will return at week 2 and week 4 of intervention for safety and compliance assessment and blood sampling (6 ml each visit) for biochemical monitoring. There will be a follow up visit 2 weeks from the end of intervention period to monitor for any adverse effects and complications and a repeat blood sampling (6ml) for biochemical monitoring.

8.4 Study population

All subjects with current overt hyperthyroidism secondary to Graves' disease who are being referred to or being followed up at Hospital Putrajaya, Hospital Queen Elizabeth II and Hospital Ampang are considered for participation. Patients are eligible for the trial if they comply with the following inclusion and exclusion criteria.

8.4.1 Inclusion criteria

- 1. Provision of written consent by subject or guardian.
- 2. Subject of either sex, more than 18 years of age
- 3. Subjects with moderate to severe overt hyperthyroidism (caused by Graves' disease).
 - Moderate to severe overt hyperthyroidism is defined as Free T₄>
 1.5 times upper limit of normal reference range and TSH below lower limit of reference range, who are either newly diagnosed or previously diagnosed and receiving ATDs currently.
 - •Graves disease is defined as hyperthyroidism coupled with clinical signs of symmetrical diffuse goiter, thyroid orbitopathy, or diffuse and vascular thyroid on ultrasound or positive TRAb antibody.
- 4. Female patients will either be
 - post-menopausal for > 2 years
 - Women of childbearing potential can be included if surgically sterile or using double contraception with at least one method being barrier contraception. Women of childbearing potential must have a negative pregnancy test at screening and at randomisation. Pregnancy tests will be repeated during each visit.

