9.8 Assessment of efficacy

• Primary efficacy endpoints are:

1. Proportion of subjects with normal thyroid hormone levels: defined as serum free T_4 or serum Free T_3 levels measured at 2 and 4 weeks after initiation of study treatment.

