11.1.2 Baseline visit (Week 0, Visit 2)

- Subjects who are eligible for the study after reviewing both inclusion and exclusion criteria will be called up for a baseline visit no longer than 1 weeks from screening visit.
- 2. Perform baseline measurements of vital signs (BP, HR, Temperature) and anthropometric measurements (Height (cm), Weight (kg) and BMI
- 3. Perform complete medical history and physical examination if not done during screening visit
- 4. Record any concomitant medications
- 5. The following baseline tests will be performed (Total of 6 mls of blood will be sampled). Thyroid function test and TRAb levels will be sent to central lab (Gribbles laboratory) whereas the other tests will be conducted at respective site.
 - a. Free T₄, Free T₃, TSH
 - b. TRAb levels
 - c. UPT (For all women of childbearing age)
 - d. ECG
 - e. ECHO if evidence of thyrotoxic cardiomyopathy
- 6. Complete relevant section/page of the CRF.
- 7. Subject who has fulfilled all inclusion and exclusion criteria and has completed baseline assessment will proceed to randomisation into any of the 3 treatment groups on the **same day**.
- 8. Refer to the study activities table below

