11.1.5 Follow up visit (Visit 5, Week 6)

Safety assessment to monitor for adverse events, monitor for symptoms and signs of adrenal insufficiency and monitor for iatrogenic hypothyroidism.

- 1. Medical history taking
- 2. Perform physical examination including vital signs
- 3. Record any AE or SAE
- 4. Obtain blood sample (total of 6 ml of blood will be sampled). Thyroid function test will be sent to central lab (Gribbles laboratory) whereas the others will be sent to respective site's laboratory. (FT₄, FT₃, TSH, Blood urea and serum electrolytes/ FBS or RBS)

Study Activities Table

	Screening	Baseline Assessment and Randomisation	Treat	ment	Follow up
Visit	1	2	3	4	5
Timeline (wks)	-1	0	2	4	6
Procedures					
Informed consent	Х				
Check eligibility	х				
Blood sample for screening ^a	х				
Randomisation		X			
Patient demographics	Х				
Medical History	х				
Complete physical exam	х				
Height (cm), Weight (kg)	х	Х	х	Х	Х
Vital signs (BP, HR, Weight, Temp)	Х	X	Х	Х	Х
FT ₄ & FT ₃ & TSH	х	X (central lab)	X (central lab)	X (central lab)	X (central lab)
TRAb levels		X (central lab)			
FBS/ RBS	Х		Х	Х	Х
BUSE	Х		Х	Х	Х
UPT ^b	х	X	Х	Х	
U/S Thyroid		Х			
ECG		Х		Х	
ECHO ^c		X			
Efficacy assessment			Х	Х	
Concomitant medication			х	Х	
Report AE and SAE			Х	Х	Х
Dispense study treatment			х	Х	
Assess compliance			х	Х	
Complete relevant section of CRF			X	Х	Х

^a HepBsAg, Anti HCV ab, HIV1/2 ab, FBC, BUSE/Creatinine, LFT, FBS/RBS, FLP. Written consent will be taken for HIV test. All blood tests on screening visit including thyroid function test will be sent to the respective site's laboratory.

^b For women of childbearing age

^c Only if clinically suggestive of thyrotoxic cardiomyopathy or has atrial fibrillation

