11.3 Sample handling and analysis

11.3.1 Collection

The only biospecimen involved in this study is blood. Blood draws of 5-10 mls would be performed as stated in the study activities table and before the dose of study drug. Blood specimen will be taken by a dedicated nurse or doctor.

The blood tests for **screening visit** will be sent to the **respective site's own laboratory.** The tests are:

- Free T₃, Free T₄, TSH
- HepBsAg, Anti HCV ab, HIV1/2 ab
- Full Blood Count
- Renal function test

- Liver function test
- Fasting blood sugar/ Random blood sugar (FBS/RBS)
- Fasting lipid profile

Subsequent FBS/RBS, renal profile for study treatment visits and follow up visits will also be sent to the respective site laboratory. Screening thyroid function tests results will not be analysed and therefore would not require specimens to be sent to a central laboratory.

Free T_4 , Free T_3 , TSH and TRAb levels for baseline and randomisation visit, study treatment visits (Visit 3 Week 2 and Visit 4 Week 4) and follow up visit (Visit 5 Week 6) will be sent to the centralised laboratory (Gribbles Pathology Laboratory Central Headquarters) for processing.

Request form with the patient's particulars shall be duly filled at the hospital site. Specimen should be individually packed in a specimen carrier bag with the request form. A call should be made by Site coordinator to Gribbles Pathology Careline number ([name]) for specimen pick up. Gribbles courier will be dispatched for specimen collection. Specimen transport will be done using a cooler bag (cool transport). Specimens will be collected by courier from the hospital site.

After checking the specimen from the courier, the laboratory staff will proceed to process the sample. Specimens are centifuged prior to sending it for analysis. Once centrifugation is done, the blood specimen is sent to the central headquarters laboratory for analysis. After test has been done, results are reviewed and if needed, validated before release.

Pre and post counselling test would be offered for HIV test in line with general practice and if positive be notified as per Malaysian law. Specimens would not be stored for future research.

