13 STATISTICAL METHODS

13.1 Sample size and power considerations

The sample sizes estimations and analyses plan were made with the caveat that the three-treatment groups comparison is as little difference from carrying out a series of three independent trials, and to use conventional significance tests without adjustment as argued by Saville (1990)²⁰. Sample size and power considerations

Sample sizes were estimated by using PASS 11 software²¹. The estimations were based on primary objectives only.

Primary objective: To achieve 80% power to detect a 30% difference in the proportions achieving normal FT_4 between Group 3 (Carbimazole+Propanolol) and each of Group 1 (Cholestyramine + Carbimazole+ Propanolol) and Group 2 (Prednisolone+ Carbimazole+ Propanolol), 41 patients are needed in each group. The proportion achieving normal FT_4 in Group 3 was estimated to be 40%. (1) Allowing for 10% drop out rate, the sample size required is therefore 45 per arm. The test statistic used is the two-sided Z test with pooled variance.

The significance level was targeted at 0.05.

Primary objective: To achieve 80% power to detect a 30% difference in the proportions achieving normal FT_3 between Group 3 (Carbimazole+Propanolol) and each of Group 1 (Cholestyramine + Carbimazole+ Propanolol) and Group 2 (Prednisolone+ Carbimazole+ Propanolol), 41 patients are needed in each group. The proportion achieving euthyroid status in Group 3 was estimated to be 40%. (1) Allowing for 10% drop out rate, the sample size required is therefore 45 per arm. The test statistic used is the two-sided Z test with pooled variance. The significance level was targeted at 0.05.

Thus, the final sample size will be 45 per group.

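### Success is a normal central-laboratory FT4 or FT3 with no condition on the Week 0 value, so patients already in range before the first dose (chiefly for FT3, which has no entry threshold) count as successes

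*Combined protocol and SAP*

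**What the plan says.** **Entry.** Section 8.4.1 requires free T4 above "1.5 times upper limit of normal reference range and TSH below lower limit of reference range", in Graves' disease. Patients may be "newly diagnosed or previously diagnosed and receiving ATDs currently". FT3 is measured at screening (section 11.1.1) but is not an entry criterion.

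**Which laboratory decides entry.** The footnote to the Study Activities Table says: "All blood tests on screening visit including thyroid function test will be sent to the respective site's laboratory". The table marks the eligibility check at Visit 1 only. Section 11.3.1 adds: "Screening thyroid function tests results will not be analysed and therefore would not require specimens to be sent to a central laboratory".

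**Baseline.** Section 11.1.2 places the baseline visit up to one week after screening. FT4, FT3 and TSH then go to the central laboratory, by courier according to section 11.3.1. A subject who meets the criteria and has "completed baseline assessment will proceed to randomisation into any of the 3 treatment groups" does so that same day. No central result is required first.

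**Success.** Section 9.8 gives the primary endpoint as "Proportion of subjects with normal thyroid hormone levels", meaning free T4 or free T3 at 2 and 4 weeks. Both are measured centrally. The central adult ranges in section 11.4 are 9-25 pmol/L for FT4 and 3-6.5 pmol/L for FT3.

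**Sizing and analysis.** Section 13.1 sizes the trial for FT4 and, separately, for a 30-point "difference in the proportions achieving normal FT_3 between Group 3" and each add-on group. Both calculations use a control rate of 40%. Section 13.2.2 plans unadjusted pairwise Z tests, by intention to treat and per protocol. No section excludes, flags or adjusts for a hormone that is already normal at Week 0.

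**The concern.** The entry rule and the responder rule do not refer to the same measurement. Entry rests on the site's FT4 and TSH at screening, while success rests on central FT4 or FT3 weeks later. For FT3, nothing at entry limits how many patients start inside 3-6.5 pmol/L. For FT4, a patient on antithyroid drugs may fall during the week before baseline, or the two laboratories may disagree.

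A patient already in range at Week 0 who stays there is a success in any arm, so carries no information on whether an add-on brings the hormone to normal. Such patients raise the success proportion in every group and reduce the difference between groups. The reported proportion also stops meaning what section 13.1 intends, which is patients who reach normal on treatment.

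**Working it through.** **Inputs.** From section 13.1: control 40%, difference 30 points (so 70% on an add-on), two-sided alpha 0.05, pooled-variance Z test, 80% power, 41 evaluable and 45 randomised per arm after 10% dropout. From section 11.4: the central ranges, and FT4 imprecision of at most 7.3% CV. Not in the documents: q, the share already normal at central baseline. It is taken as 5 to 30%, and those patients are assumed to stay normal in every arm.

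**The plan's own figure.** n = [1.96√(2 × 0.55 × 0.45) + 0.8416√(0.24 + 0.21)]² / 0.30² = 41.97, so 42 against 41 stated. Power at 41 is 0.790 by this approximation (0.813 by exact binomial calculation). 41/0.9 = 45.6, so 46 against 45 stated. The plan reproduces to within one patient per arm.

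**Power formula.** Power = Φ{[Δ√n − 1.96√(2p̄(1 − p̄))] / √[pC(1 − pC) + pT(1 − pT)]}, where Δ = pT − pC and p̄ is their mean.

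**Reading A: 40% v 70% applies only to patients abnormal at baseline.** Then pC = q + 0.4(1 − q), pT = q + 0.7(1 − q) and Δ = 0.30(1 − q). The restricted analysis keeps 40% v 70% with n = 41(1 − q).

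| q | Control | Add-on | Difference (points) | Power, all 41 | Restricted n | Power, restricted |
|---|---|---|---|---|---|---|
| 0% | 40.0% | 70.0% | 30.0 | 0.79 | 41.0 | 0.79 |
| 5% | 43.0% | 71.5% | 28.5 | 0.75 | 38.9 | 0.77 |
| 10% | 46.0% | 73.0% | 27.0 | 0.71 | 36.9 | 0.75 |
| 20% | 52.0% | 76.0% | 24.0 | 0.62 | 32.8 | 0.69 |
| 30% | 58.0% | 79.0% | 21.0 | 0.54 | 28.7 | 0.63 |

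Example at q = 10%: (0.27√41 − 1.96√(2 × 0.595 × 0.405)) / √(0.2484 + 0.1971) = (1.729 − 1.361)/0.667 = 0.55, and Φ(0.55) = 0.71.

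**Reading B: 40% v 70% already includes baseline-normal patients.** All-patient power stays at 0.79 for any q. Among patients abnormal at baseline the rates are (0.4 − q)/(1 − q) and (0.7 − q)/(1 − q).

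| q | Control | Add-on | Difference (points) | Restricted n | Power, restricted |
|---|---|---|---|---|---|
| 5% | 36.8% | 68.4% | 31.6 | 38.9 | 0.81 |
| 10% | 33.3% | 66.7% | 33.3 | 36.9 | 0.83 |
| 20% | 25.0% | 62.5% | 37.5 | 32.8 | 0.88 |

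Under both readings the restricted comparison has more power than the all-patient one, despite the smaller n.

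**Chance imbalance.** The SD of the between-arm difference in the baseline-normal share is √[2q(1 − q)/41], or 6.6 points at q = 10% and 8.8 at 20%. This is part of ordinary sampling error, but restriction or baseline adjustment would remove it.

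**How likely is a normal central FT4 at Week 0?** Take a patient whose site reading is exactly 1.5 × ULN (37.5 pmol/L on the central scale), and assume a 7.3% CV in both laboratories. The chance of a central reading at or below 25 is Φ[ln(25/37.5)/(0.073√2)] = Φ(−3.93), about 0.00004. Imprecision alone does not produce it; a real fall or a systematic difference between laboratories is needed. No such bound exists for FT3.

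**The case against.** The strongest reply is that the size is unknown. The documents give q for neither hormone and do not say whether the 40% includes baseline-normal patients. A fall below the planned 30 points is therefore conditional: under Reading B planned power is untouched. Even under Reading A, at q = 2% the all-patient and restricted powers are 0.775 and 0.782, a negligible gap. All of this stands.

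Randomisation also balances these patients on average, so the intention-to-treat comparison remains valid. That stands too. A reader might infer that the endpoint favours one arm; nothing in the documents supports that.

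A reader might also infer that a site whose upper limit is below the central 25 pmol/L admits patients already near or inside the central normal range for FT4. The documents do not support this. Section 8.4.1 states the threshold as a multiple of the upper limit, and neither site ranges nor site assays are given. A lower site limit may simply reflect a lower-reading assay, in which case 1.5 times it corresponds to about 37.5 pmol/L centrally. Nor is entry judged on FT4 by itself, since section 8.4.1 also requires a low TSH.

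Finally, restricting the set departs from the planned all-randomised denominator. Adjusting for central baseline FT4 or FT3 would keep every patient and is a reasonable supporting analysis. It would not change what a success means for a patient who started in range.

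**Conclusion.** The gap is real: no section makes an abnormal central Week 0 value a condition of entry, of success or of inclusion in the analysis. It bears mainly on FT3, which has no entry threshold. For FT4 a normal central baseline is possible, particularly in patients already on antithyroid drugs, but probably uncommon.

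The harm is dilution, inflated absolute rates and chance imbalance. Under Reading A, power at 41 per arm is 0.75, 0.71 and 0.62 at q = 5, 10 and 20%, against 0.77, 0.75 and 0.69 in the restricted set. Under Reading B it stays at 0.79, and restriction raises it to 0.81, 0.83 and 0.88. These figures rest on an assumed q and on baseline-normal patients staying normal. They do not show that the trial is underpowered. They show that restriction helps on either reading and that the plan should settle the matter in advance.

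**What to change.** For each hormone, pre-specify the comparison among all randomised patients above the central upper limit at the Week 0 pre-dose sample (FT3 > 6.5 pmol/L, FT4 > 25 pmol/L). Define success as a value within the central range at the assessment visit. State how a missing Week 0 result is handled.

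Keep the present all-randomised endpoint exactly as it is as a sensitivity analysis. Baseline-normal patients must not be recoded there as failures, or that analysis would no longer reproduce the planned endpoint. Report by arm the number already normal for each hormone at Week 0.

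The set is fixed by a value sampled before randomisation, so treatment cannot influence who is in it. It should be written down before outcomes are seen, because the same restriction added later would look post hoc.

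Cost: no new visit or test, as the sample is already planned. The denominator becomes smaller, mainly for FT3, and differs between the hormones. Restriction does not restore 80% power under Reading A. Keeping 41 evaluable baseline-abnormal patients per arm after 10% dropout would need 41/[0.9(1 − q)] randomised, which is 48, 51 and 57 per arm at q = 5, 10 and 20%, against 45 planned. Whether to enlarge the trial can be decided separately from the change in definition.

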Three treatment modalities are currently available for the management of hyperthyroidism: antithyroid drugs (ATDs), surgery, and radioactive iodine (RAI) therapy. Treatment for hyperthyroidism is aimed at restoring euthyroidism with ATDs while awaiting disease remission and resolution of autoimmunity or inducing permanent hypothyroidism with subsequent thyroxine replacement by total thyroidectomy or RAI therapy. Beta-blockers (for example propanolol and atenolol) are added to block beta-adrenergic tone for symptomatic relief of palpitations, tachycardia, tremulousness, anxiety, heat intolerance, fatigability and shortness of breath. There is currently no consensus on the "best" treatment option with various practices in different centers and countries. The choice of treatment depends on the cause of hyperthyroidism, patient's age and preference, severity of disease, glandular size, activity and severity of Graves' opthalmopathy, local practices and resources.

ATDs including methimazole, carbimazole, and propylthiouracil are effective treatments that inhibit thyroid hormone synthesis, and have clinically important immunosuppresive effects including reducing serum antithyrotropin receptor antibody concentration with time. Antithyroid drugs are an effective treatment option but these drugs take in most cases between 6 to 8 weeks to achieve euthyroidism. It has also shown to have the highest relapse rate at 52.7% compared to RAI (15%) and surgery (10%) in a recent meta analysis⁸. In addition 13% of patients on ATDs experienced adverse events with rash most common with methimazole and hepatic involvement with propylthiouracil⁸.

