9.3 Concomitant medication/treatment

A concomitant medication is any medicatiom, other than the trial product, which is taken during the trial. Details of any concomitant medication must be recorded at visit 1. Changes in concomitant medication must be recorded at each subsequent visit as they occur.

Concomitant medications that are not permitted during the study period

Plasma levels and efficacy of prednisolone may be affected by the concomitant use amphotericin B, anticholinesterase agents, CYP 3A4 inducers (e.g. barbiturates, phenytoin, carbamazepine, and rifampin), CYP 3A4 inhibitors (e.g., ketoconazole, macrolide antibiotics), cyclosporine and digitalis. Lithium, Propylthiouracil, Lugols iodine, Contrast medium are not permited as it will affect the results of the study.

Cautious use of phenylbutazone, warfarin, thiazide diuretics (acidic) as well as tetracycline penicillin G, phenobarbital, thyroid and thyroxine preparations, estrogens and progestins and digitalis as cholestyramine resin may delay or reduce the absorption of these drugs.

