9.4 Treatment allocation and randomization

A participant will be randomly allocated to one of the three treatments per random allocation sequence that will be generated by a member of the study team. The allocation ratio is 1:1:1. The random allocation sequence will the Web site Randomization.com be generated by using (http://www.randomization.com). Blocked randomisation will be used. The random allocation sequence will be generated by a member of the study team who will not be involved in the enrolment of subjects and assessment of outcomes. The block size of 6 will be used. The allocation sequence generated will be will be concealed in an opaque sealed envelope with the following information written:

Front page

- 1. Study title
- 2. Site name and code

- 3. Study PI name
- 4. Protocol number
- 5. Sequential randomization number

Inside the randomization envelope

- 1. Study title
- 2. Site name and code
- 3. Study PI name
- 4. Protocol number
- 5. Sequential randomization number
- 6. Subject ID
- 7. Date and time the envelope open
- 8 Signature and name of the person opening the envelope
- 9. Study treatment the patient is allocated to

The identity of the treatment that will be assigned to each subject will only be revealed on the first day of treatment. Principal Investigator and/or Sub Investigator will screen and enrol the subjects. Principal Investigator and/or Sub Investigator will assign the treatment to each subject, according to the allocation sequence.

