13.2.2 Efficacy Analysis

1. For the primary objectives, all comparisons of means between treatment will be analysed using one-way ANOVA and all pairwise comparisons of proportions will be analysed by using two-sided Z test and 95% confidence interval of the estimated difference will be calculated. Alpha level will be set at 0.05 and no adjustment will be made for the multiple pairwise comparisons. Analysis will be based on intention to treat and per protocol analysis.

2. For secondary objectives, all comparisons of means between treatment will be analysed using one-way ANOVA and all comparison of proportions will be analysed using chi-square test of independence.

Alpha level will be set at 0.05. Analyses will be based on safety set analysis.

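### Current antithyroid drug use at entry is likely to be prognostic for a 2- and 4-week endpoint, but neither the randomisation nor the primary test takes it into account

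*Combined protocol and SAP*

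**What the plan says.** Section 8.4.1 of the combined protocol and SAP admits subjects "who are either newly diagnosed or previously diagnosed and receiving ATDs currently", provided free T4 exceeds 1.5 times the upper limit of normal and TSH is low. It sets no limit on which drug or for how long. No run-in is described; eligible subjects are "called up for a baseline visit no longer than 1 weeks from screening visit".

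Section 6 says of antithyroid drugs that "these drugs take in most cases between 6 to 8 weeks to achieve euthyroidism". Under 9.8 the primary endpoint is the proportion with normal hormone levels, "measured at 2 and 4 weeks after initiation of study treatment".

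On allocation, 9.4 states "Blocked randomisation will be used" and "The block size of 6 will be used". The envelopes carry a site name and code, but no stratification factor is named. On analysis, 13.2.2 states that "all pairwise comparisons of proportions will be analysed by using two-sided Z test", with a 95% confidence interval and no covariate, stratum or subgroup. Section 13.1 uses one control rate, 40%, for the whole population. Section 13.2.1 compares baseline characteristics descriptively, and 11.1.1 takes a medication history at screening.

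On medicines during the study, 9.3 states "Lithium, Propylthiouracil, Lugols iodine, Contrast medium are not permited as it will affect the results of the study". Section 6 counts propylthiouracil among the antithyroid drugs.

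**The concern.** If most patients need 6 to 8 weeks of drug to become euthyroid, time already on drug bears on who is normal at weeks 2 and 4. Take a subject randomised after four weeks of treatment. The two readings fall at about weeks 6 and 8 of that subject's course, whereas a newly diagnosed subject is read at weeks 2 and 4. A subject still above the entry threshold after long treatment may instead be a poor responder. The free T4 threshold narrows severity at entry but does not separate these histories.

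Blocking fixes the arm sizes, not the mix of histories within them. If one arm happens to receive more already-treated subjects, the observed difference in proportions shifts. The planned baseline table might show this, but no planned analysis would correct for it. The plan thus leaves unused a factor that its own background suggests is informative and that is already recorded.

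**Working it through.** **The plan's own figure.** Inputs from 13.1: 40% against 70%, two-sided alpha 0.05, 80% power, pooled variance.

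n = [1.96·√(2·0.55·0.45) + 0.842·√(0.40·0.60 + 0.70·0.30)]² / 0.30² = 41.97, so 42 per group.

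The plan states 41, at which the formula gives 79.0% power. With 10% dropout, 41/0.9 = 45.6 against 45 stated. Both agree within one patient, so the sample size is not at issue here.

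**Assumptions.** The documents give neither the share already treated (s) nor the difference in success by prior treatment (d). I take s = 30% and 50%, and d = 20, 30 and 40 points, with an average success rate of 40%.

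**Chance imbalance between two arms of 45.** SD = √(2·s·(1−s)/45).

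- s = 0.3: √(0.42/45) = 9.7 points
- s = 0.5: √(0.50/45) = 10.5 points

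From exact binomial calculation, the chance per pair of arms of an imbalance of at least 10 points is 30-34%, and of at least 15 points 13-17%.

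**Shift in the treatment difference.** The 95% range is ±1.96·SD·d. For s = 0.3 and d = 0.2 this is 1.96 × 0.0966 × 0.2 = 3.8 points.

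**The interval that already contains it.** With 40% in both arms, the unadjusted half-width is 1.96·√(2·0.24/45) = 20.2 points. Prior treatment explains a fraction s(1−s)d²/0.24 of the outcome variance, so full adjustment multiplies the half-width by √(1 − that fraction).

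| s | d (points) | 95% shift (points) | Variance explained | Adjusted half-width (points) | Reduction |
|---|---|---|---|---|---|
| 30% | 20 | ±3.8 | 3.5% | ±19.9 | 1.8% |
| 30% | 30 | ±5.7 | 7.9% | ±19.4 | 4.0% |
| 30% | 40 | ±7.6 | 14.0% | ±18.8 | 7.3% |
| 50% | 20 | ±4.1 | 4.2% | ±19.8 | 2.1% |
| 50% | 30 | ±6.2 | 9.4% | ±19.3 | 4.8% |
| 50% | 40 | ±8.3 | 16.7% | ±18.5 | 8.7% |

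**Error and power.** A simulation with 41 per arm and 200,000 runs per setting compared the unadjusted pooled Z test with a Cochran-Mantel-Haenszel test stratified by prior treatment. Each cell gives unadjusted / stratified, in percent.

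| s | d (points) | Type I error, all trials | Type I error given imbalance ≥15 points | Power for a 30-point effect |
|---|---|---|---|---|
| 30% | 20 | 5.5 / 5.0 | 7.1 / 5.2 | 81.3 / 80.3 |
| 30% | 30 | 5.4 / 4.9 | 8.5 / 5.0 | 81.3 / 82.2 |
| 30% | 40 | 5.5 / 5.0 | 10.9 / 5.0 | 81.3 / 85.0 |
| 50% | 20 | 5.5 / 5.0 | 7.0 / 5.0 | 81.3 / 80.5 |
| 50% | 30 | 5.5 / 5.0 | 8.5 / 5.0 | 81.3 / 82.8 |
| 50% | 40 | 5.4 / 4.8 | 10.8 / 5.0 | 81.2 / 86.2 |

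The unadjusted overall error does not change with d, because each arm's success count stays binomial at 40%. The small excess over 5% therefore comes from the test at this sample size, not from prior treatment. The already-treated were given the lower success rate. At s = 50% the direction is immaterial because the two groups are interchangeable; at 30% the reverse was not simulated. At 41 per arm the chance of an imbalance of at least 15 points is 12-15%.

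**The case against.** The strongest reply is that randomisation already deals with this. Imbalance averages out, the unadjusted test is near nominal overall, and the ±4 to ±8 points are part of the ±20-point sampling error, not an addition to it. That stands. A reader might infer that the primary comparison is systematically biased or invalid; the documents do not support that.

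The prognostic effect is also assumed. Part-treated subjects may normalise sooner while poor responders do worse, and within one already-treated group these may partly cancel. That stands too: the true net difference could lie below 20 points, and a yes/no factor does not capture duration or resistance.

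A mixed population fits the rationale. Section 6 names failure of antithyroid drugs as a situation for adjuncts, and its hypothesis of faster euthyroidism is not confined to the start of treatment. A reader might infer that enrolling both groups contradicts the hypothesis, or that the drugs have no action before 6 weeks. Section 6 supports neither: its figure is the time to euthyroidism.

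The absence of a wash-out is not treated as a defect here. Whether to withhold drug is a clinical question on which no position is taken.

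Finally, 9.3 governs medicines during the study and is not an eligibility rule, so it can coexist with 8.4.1. What remains is that the handling of subjects entering on propylthiouracil is unstated.

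None of this removes the narrower point. The factor is recorded and plausibly prognostic on the plan's own premise, and no planned analysis uses it.

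**Conclusion.** The point holds as a worthwhile, inexpensive improvement in precision and in protection against an unlucky allocation. It would not by itself create or remove a 30-point difference, but it could matter for a borderline result.

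Under the assumed shares (30-50%) and differences (20-40 points), stratified analysis narrows the half-width by about 2-9%. It holds error near 5% in the 13-17% of pairwise comparisons with an imbalance of at least 15 points, where the unadjusted test rejects a true null about 7-11% of the time. Power is about 80-86% against about 81%. At a 20-point difference the stratified test shows no power gain, at 80.3-80.5% against 81.3%. The main uncertainty is the size and direction of the prior-treatment effect.

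**What to change.** 1. In 13.2.2, make each pairwise comparison of proportions stratified by receipt of an antithyroid drug at screening (yes/no), for example a Mantel-Haenszel risk difference with 95% confidence interval. Show the result in each stratum descriptively, without separate significance claims.
2. Tabulate status, drug and weeks of treatment by arm in the 13.2.1 baseline comparison, since the yes/no factor does not capture duration.
3. If envelopes are not yet made, prepare separate runs in 9.4 for the two groups at each site. If they are made, the stratified analysis alone is enough.
4. Reconcile 8.4.1 with 9.3 for subjects who enter on propylthiouracil, and state how they are handled.

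The cost is a sentence or two in the analysis section and, optionally, a second envelope run per site; the medication history is already taken at visit 1. No patients are added. The downsides are a few more incomplete blocks and no power gain if prior treatment proves only weakly prognostic.
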